9.2.13 Biomarker Analysis

Blood samples will be collected at Visit 1 and Visit 9 (if appropriate considering the patients' weight [patient must weigh \geq 16 kg at Visit 1] - [Section 9.2.10](#)) for the analysis of exploratory biomarkers. This may include BDNF, TNF α , interferon-gamma and interleukins, and/or other biomarkers implicated in RTT, as indicated by emerging research. IGF-1 may also be a biomarker implicated in RTT and will be measured as part of the clinical laboratory sampling panel. Samples for biomarker research will be stored for a maximum of 5 years from the date of the Last Patient's Last Visit, after which they will be destroyed; they will only be used for the purpose they were collected. Samples from patients who are screen failures will not be tested and will be destroyed and no genetic testing will be performed on any of the biomarker samples.

The results of this biomarker research may be reported either in the clinical study report itself or as an addendum, or separately in a scientific report or publication. The results of this biomarker research may be pooled with biomarker data from other studies with the IMP to generate hypotheses to be tested in future research.

Study Code: GWND18064

EudraCT Number: 2018-003370-27

Clinical Protocol 4.1, 07Jul2020 (duplicate synopsis removed)

9.2.14 Randomization and Trial Supply Management System

The RTSM system will be used to assign patients to treatment arms, manage IMP supply, and to provide treatment allocation information in the event of patient unblinding. The RTSM system information can be accessed via the eCRF.

A member of the trial team must register in the eCRF each clinic visit in order to:

- Obtain a patient's number (Visit 1).
- Randomize a patient (Visit 2).
- Obtain dispensing information (Visits 2, 5, 6, 7, 8 and 9).
- Provide completion/taper/premature termination information (Visit 9/the withdrawal visit or Visit 10, as applicable).

Training will be given to all sites prior to the start of the trial.

9.2.15 Dosing Diary/Compliance Review

Caregivers will be provided with a dosing schedule. Information on IMP administration will be collected daily from Visit 2 to Visit 10. Caregivers will be asked if the patient has taken their IMP as per the dosing schedule for that day; information will be collected electronically. Dosing compliance will be reviewed at each clinic visit. Any discrepancies will be discussed with the caregiver and documented accordingly within the patient's source documents. As part of the compliance review caregivers will be asked at the visits about the time of IMP administration in relation to meals.

9.2.16 Symptom Diary

The completion of an electronic symptom diary will be required from screening to Visit 9 (completed weekly). Caregivers will be asked to rate on a 0–10 numerical rating scale (NRS) the patient's condition and performance/severity of symptoms in terms of breathing, hand stereotypies, interactions, problem behaviors, constipation, seizures and sleep.

At Visit 1, caregivers will be trained on the weekly electronic diary completion.

The symptom diary will be reviewed at each clinic visit. Any discrepancies will be discussed with the caregiver and documented accordingly within the patient's source documents.

Study Code: GWND18064

EudraCT Number: 2018-003370-27

Clinical Protocol 4.1, 07Jul2020 (duplicate synopsis removed)

To ensure consistency it is advised that an identified main caregiver completes all necessary diaries throughout the trial.

The diary will be completed electronically.

9.2.17 Questionnaires and Assessments Completed at Scheduled Visits

Caregiver questionnaires and the symptom diary should be completed by an identified main caregiver, nominated at Visit 1. This should be a person able to assess the patient based on daily contact and most likely to be able to attend study visits. The same person should answer/complete the questionnaires/assessments in order to maintain consistency. The identified caregiver will also receive training on completion of caregiver questionnaires. Questionnaires should be completed during the scheduled visits under the supervision of a trained and delegated member of the investigator team.

To ensure consistency, investigator-completed questionnaires should be completed for each patient by the same investigator throughout the trial. Investigators must have completed the sponsor specified training for each questionnaire, before any questionnaires are completed.

9.2.17.1 Rett Syndrome Behavior Questionnaire

The RSBQ is a caregiver-completed questionnaire that measures the frequency of current disease characteristics (45 items) that may or may not apply to the patient (see [Appendix 3.5](#)). Each item is rated on a 3-point numerical scale; 0 indicating an item that is ‘not true as far as you know’, 1 indicating an item is ‘somewhat or sometimes true’, and 2 indicating an item that is ‘very true or often true’. The total maximum score is 90 and higher total scores represent greater severity. It encompasses 8 subscales: general mood, breathing problems, hand behaviors, face movements, body rocking/expressionless face, night-time behaviors, anxiety/fear, and walking/standing⁵⁴.

9.2.17.2 Clinical Global Impressions Questionnaire

The clinical global impressions (CGI) questionnaire was developed as a clinical trial measure to provide a brief, stand-alone assessment of the clinician’s view of the patient’s global functioning prior to and after initiating a study medication⁵⁵.

The CGI questionnaire is split into 2 scales; the CGI-S scale and the CGI-I scale (see [Appendix 3.3](#) and [Appendix 3.4](#)). The CGI-S is a 7-point scale that requires the clinician to rate the severity of the patient’s illness at the time of assessment, relative to the

Study Code: GWND18064

EudraCT Number: 2018-003370-27

Clinical Protocol 4.1, 07Jul2020 (duplicate synopsis removed)

clinician's experience with patients who have the same diagnosis. Considering total clinical experience, a patient will be assessed on severity of illness at the time of rating. This is rated as: 1 = normal, not at all ill; 2 = borderline ill; 3 = mildly ill; 4 = moderately ill; 5 = markedly ill; 6 = severely ill; or 7 = extremely ill. The second section, the CGI-I, is a 7-point scale that requires the clinician to assess how much the patient's illness has improved or worsened relative to a baseline state at the beginning of the intervention. This is rated as: 1 = very much improved; 2 = much improved; 3 = minimally improved; 4 = no change; 5 = minimally worse; 6 = much worse; or 7 = very much worse.

To ensure consistency, investigators will be instructed to complete the CGI referring to a pre-defined set of anchors developed specifically for the use of the CGI in RTT⁵⁸.

The CGI-S and CGI-I assessments should be based on the entirety of the visit.

9.2.17.3 Rett Syndrome Motor-Behavioral Assessment Scale

The MBA-9 scale is completed by the investigator and evaluates 9 RTT symptoms. MBA-9 was derived from the full MBA scale (37 RTT symptoms) by selecting the items that are deemed to be amenable to change and that reflect areas of meaningful clinical change. It includes 5 questions from the original Behavioral/Social Assessment, 1 question from the Orofacial/Respiratory Assessment and 3 questions from the Motor Assessment/Physical Signs (see [Appendix 3.2](#)). The severity of current symptoms are rated on a 5-point numerical scale; 0 = normal or never; 1 = mild or rare; 2 = moderate or occasional; 3 = marked or frequent; 4 = very severe or constant. The total maximum score is 36 and higher total scores represent greater severity⁶⁰. The MBA items address core symptoms of RTT.

9.2.17.4 Clinical Severity Scale

The CSS consists of a composite score based on 13 individual, ordinal categories measuring clinical features common in RTT. All scores range from 0-4 or 0-5 with 0 representing the least severe and 4 or 5 representing the most severe finding (see [Appendix 3.1](#))⁶⁸.

The CSS will be administered at Visit 1 to evaluate disease severity. A minimum total score of 10 and a maximum total score of 36 are required for eligibility. At randomization, all patients will be stratified by severity, based on their CSS score (either a CSS score within the range of 10–22, or a CSS score within the range 23–36).

Study Code: GWND18064

EudraCT Number: 2018-003370-27

Clinical Protocol 4.1, 07Jul2020 (duplicate synopsis removed)

9.2.17.5 SF-36

Caregivers health-related quality of life will be assessed using the SF-36 questionnaire (see [Appendix 3.6](#)). SF-36 measures 8 domains of health-related quality of life within 8 scales: 1) limitations in physical activities because of health problems; 2) limitations in social activities because of physical or emotional problems; 3) limitations in usual role activities because of physical health problems; 4) bodily pain; 5) general mental health (psychological distress and well-being); 6) limitations in usual role activities because of emotional problems; 7) vitality (energy and fatigue); and 8) general health perceptions. The domains are used to calculate composite scores - physical health composite score (PCS) and mental health composite score (MCS). The scores for the SF-36 are based on a 0 to 100 scale; zero represents the lowest possible score, and 100 represents the highest possible score, with higher score indicating a better health state.

9.2.17.6 CHQ-PF50

The CHQ-PF50 is a generic QoL instrument designed and normed for children from 5 to 18 years of age. This instrument is a well-validated general QoL measure in pediatric populations with chronic illness. It measures QoL of the child and the family by parent or child report. The caregiver will be asked to complete the questionnaire on behalf of the patient. The CHQ-PF50 covers multidimensional health concepts including: Physical Functioning, Role/Social Limitations–Emotional/Behavioral, Role/Social Limitations–Physical, Behavior, Mental Health, Self-Esteem, General Health, Bodily Pain, Family Activities, Parent Impact–Time, Parent Impact–Emotional, and Family Cohesion. The CHQ-PF50 provides subscale scores as well as a Standardized Physical Summary (PhS) score and standardized Psychosocial Summary (PsS) score. Scores are based on a 0 to 100 scale and higher scores indicate better quality of life.

9.2.17.7 Hospital Services Use Questionnaire

This is a health utilization questionnaire designed to analyze the frequency of patient hospitalizations and hospital visits (see [Appendix 3.8⁷³](#)). Hospitalizations will also be recorded in the patient's eCRF and through the serious adverse event (SAE) reporting process. The questionnaire will be completed via caregiver interview.

9.2.17.8 Children's Sleep Habit Questionnaire

This is a caregiver completed sleep screening instrument designed for school-aged children⁹. The CSHQ includes 33 items within eight subscales reflecting the following sleep domains: 1) Bedtime Resistance, 2) Sleep Onset Delay, 3) Sleep Duration, 4) Sleep

Study Code: GWND18064

EudraCT Number: 2018-003370-27

Clinical Protocol 4.1, 07Jul2020 (duplicate synopsis removed)

Anxiety, 5) Night Wakings, 6) Parasomnias, 7) Sleep-Disordered Breathing, 8) Daytime Sleepiness. Caregivers are to answer based on the last week. If the last week was unusual for a specific reason, the caregiver should choose the most recent typical week. The answers to each question are provided by a choice of 3 markers: “Usually” if it occurs 5 or more times in a week; “Sometimes” if it occurs 2 to 4 times in a week; “Rarely” if it occurs never or 1 time in a week. Some items should be reversed in scoring, so that a higher score reflects more disturbed sleep behavior (see [Appendix 3.10](#)). The caregiver is also asked to indicate for each item if the sleep item is a problem.

9.2.17.9 Suicidality Assessment

The profound cognitive impairment of RTT patients is such that the Children’s Columbia-Suicide Severity Rating Scale is not considered appropriate in this trial. Instead, suicidality will be assessed by the investigator via a clinical interview with the caregiver (see [Appendix 3.9](#)).

9.2.18 Tanner Staging

The pubic hair (both sexes), genital (males only) and breast (females only) growth of all adolescent patients (i.e., \geq 7 years of age⁷⁰ at the time of signing the informed consent form, or earlier if clinically indicated by onset of menarche or other signs of precocious puberty) will be assessed using Tanner Staging (see [Appendix 3.7](#))⁷². The assessment can either be performed by examination during the study visit or the appropriate Tanner Stage can be indicated by the caregiver, with reference to the chart provided.

Once a patient reaches a score of V (i.e., 5) the assessment need not be performed again.

9.2.19 Investigational Medicinal Product Accountability

Records of IMP accountability will be maintained according to [Section 5.3.4](#).

IMP will be dispensed at each of the following visits:

- Visit 2 (Day 1)
- Visit 5 (Day 29)
- Visit 6 (Day 57)
- Visit 7 (Day 85)
- Visit 8 (Day 127)

Study Code: GWND18064

EudraCT Number: 2018-003370-27

Clinical Protocol 4.1, 07Jul2020 (duplicate synopsis removed)

- Visit 9 (Day 169)

Caregivers will be asked to return all IMP (used and unused) to each relevant visit (Visits 5, 6, 7, 8, 9, 10). The site will check the returned IMP against the expected usage as per daily dosing diary. Any discrepancies will be discussed with the caregiver and documented accordingly within the patient's source documents.

9.2.20 Adverse Events

All AEs will be recorded on the eCRF. All AEs* occurring during the trial, whether or not attributed to the IMP, observed by the investigator or reported by the patient will be recorded in the eCRF, questioning the patient further if necessary.

*For the patient's expected seizure types, these do not routinely require documentation as AEs. However, any worsening, including change in the pattern or severity of seizures should be documented in the eCRF if deemed to meet the definition of an AE, in the investigator's opinion.

Any AE which meets SAE criteria should still be reported as a SAE.

SAEs must be reported to GW Pharmacovigilance Department (PVD) within 24 hours of discovery or notification of the event via recording in the eCRF.

Refer to [Section 12](#) for definitions, procedures and further information on AE reporting.

9.3 Special Circumstances

During special circumstances (e.g., COVID-19 pandemic), the specific guidance from local public health and other competent authorities regarding the protection of individuals' welfare must be applied. In cases where participants are not able to perform all protocol-defined assessments due to special circumstances, the investigator must discuss with the medical monitor potential mitigation approaches.

For the duration of such special circumstances, the following measures may be implemented for enrolled subjects:

- Safety follow-up may be done by a telephone call, other means of virtual contact or home visit, if appropriate.
- Patient and/or clinician-rated outcomes assessments may be done by videoconference, telephone call, other means of virtual contact, if possible.

Study Code: GWND18064

EudraCT Number: 2018-003370-27

Clinical Protocol 4.1, 07Jul2020 (duplicate synopsis removed)

- Visits may take place in a different location than defined in the protocol. If this is not feasible, then the visit may take place virtually with documentation of the means of communication (e.g., phone call or videoconference).
- An alternative approach for IMP dispensing, secure delivery, and collection may be used.
- Biological samples may be collected and analysed at a different location than defined in the protocol. Biological samples should not be collected if they cannot be processed in a timely manner or appropriately stored until shipping/processing.
- If despite best efforts it is not possible to collect the biological samples or safety assessments (e.g., ECG, vital signs) within the interval predefined in the protocol (see [APPENDIX 1](#)), then the interval may be extended up to a maximum length of 14 days.
- If despite best efforts a safety assessment cannot be performed, the investigator must review the benefit-risk for patient continuation in the study and record this in the medical records.

The rationale (e.g., the specific limitation imposed by the special circumstances that led to the inability to perform the protocol-specified assessment) and outcome of the discussion with the medical monitor will be documented in the medical record.

Information on how each visit was performed will be recorded in the eCRF.

Study Code: GWND18064

EudraCT Number: 2018-003370-27

Clinical Protocol 4.1, 07Jul2020 (duplicate synopsis removed)

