Appendix 3.2 9-items Motor-Behavioral Assessment Scale

An example of the 9-items Motor-Behavioral Assessment (MBA-9)⁶⁰ scale is shown below.

1. Regression of motor skills

- 0 None
- 1 Dyspraxia of gait and hand use including bilateral pincer grasps
- 2 Able to walk and use one or both hands
- 3 Able to walk independently or with support or to use one or both hands
- 4 No motor skill

2. Poor eye/social contact

- 0 None
- 1 25% of time
- 2 50% of time
- 3 75% of time
- 4 100% of time

3. Lack of sustained interest

- 0 None
- 1 25% of time
- 2 50% of time
- 3 75% of time
- 4 100% of time

4. Does not reach for objects or people

- 0 None
- 1 25% of time
- 2 50% of time
- 3 75% of time
- 4 100% of time

5. Chewing difficulties (by history at time of assessment)

- 0 None
- 1 Coarse chopped
- 2 Fine chopped
- 3 Pureed or mashed
- 4 Gastrostomy

Study Code: GWND18064
EudraCT Number: 2018-003370-27
Clinical Protocol 4.1, 07Jul2020 (duplicate synopsis removed)

6. Speech disturbance

- 0 Fluent
- 1 Phrases/sentences
- 2 Words with meaning or intention
- 3 Vocalizations, no words
- 4 No utterances

7. Hand clumsiness (by history or at time of assessment)

- 0 Purposeful hand use
- 1 Plays with toys or activates switches purposefully
- 2 Uses utensils/cup, may be adaptive
- 3 Finger feeds only
- 4 No purposeful hand use

8. Dystonia

- 0 None
- 1 Focal dystonia, one joint
- 2 Focal dystonia, more than one joint
- 3 Generalized dystonia, > 2 extremities
- 4 Fixed positional deformity

9. Hypertonia/rigidity

- 0 None
- 1 Ankle hypertonia/rigidity
- 2 Upper or lower limb hypertonia/rigidity
- 3 Generalized hypertonia without contractures
- 4 Generalized hypertonia with contractures

Study Code: GWND18064
EudraCT Number: 2018-003370-27
Clinical Protocol 4.1, 07Jul2020 (duplicate synopsis removed)

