### 8.3.3 MBA-9

The MBA-9 scale is completed by the investigator and addresses core symptoms of RTT. MBA-9 was derived from the full MBA scale (37 RTT symptoms) by selecting the items that are deemed to be amenable to change and that reflect areas of meaningful clinical change. The severity of current symptoms is rated on a 5-point numerical scale; 0 = normal or never; 1 = mild or rare; 2 = moderate or occasional; 3 = marked or frequent; 4 = very severe or constant. The MBA-9 score is calculated by summing the scores of the individual items. The maximum score is 36 and higher scores represent greater severity.

MBA-9 scores and their change from baseline will be summarized by treatment and visit.

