#### **9.4.6 Patients Impacted by COVID-19**

A listing of all patients impacted by COVID-19 related study disruption will be provided. The listing will include patient ID, site and a description of how the patient's participation was altered.

Protocol Deviations related to COVID will be provided in a data listing.

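### Telephone MBA-9 ratings, for which six of nine items cannot be seen or examined, enter the same change-from-baseline summary as in-person ratings, with blank items filled by LOCF

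*Protocol*

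**What the plan says.** Protocol section 9.3 relaxes the conduct rules in special circumstances such as the pandemic: "Patient and/or clinician-rated outcomes assessments may be done by videoconference, telephone call, other means of virtual contact, if possible". No scale is excepted. The same section adds: "Information on how each visit was performed will be recorded in the eCRF".

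Protocol section 9.2.17.3 describes the scale: "The MBA-9 scale is completed by the investigator and evaluates 9 RTT symptoms". On scoring it states: "The total maximum score is 36 and higher total scores represent greater severity". The schedule of assessments places the MBA-9 at Visits 2, 7 and 9 only. On the form in Protocol Appendix 3.2 two items carry a history label: "5. Chewing difficulties (by history at time of assessment" and, for item 7, "Hand clumsiness (by history or at time of assessment". The other seven carry none.

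The analysis in SAP section 8.3.3 is one sentence: "MBA-9 scores and their change from baseline will be summarized by treatment and visit". SAP section 6.1.2 makes Visit 2 the efficacy baseline. SAP section 6.1.1 tabulates data under the visit at which they were recorded, without further derivation. SAP section 6.1.7.1 names the MBA-9 as a questionnaire without subscales, whose missing items are filled by LOCF. On the pandemic, SAP section 9.4.6 says: "A listing of all patients impacted by COVID-19 related study disruption will be provided".

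**The concern.** The MBA-9 was chosen as a clinician's assessment of motor and behavioural signs (Protocol section 3.3.1.2). Over the telephone the clinician can see and examine nothing. For most of the scale, either the caregiver's account replaces the clinician's observation or the item is left blank.

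The SAP treats neither case separately. A score based on caregiver report is subtracted from a Visit 2 score that would normally have been obtained in clinic, where the first dose is given. A blank item is filled with an earlier score. Both results go into the by-visit summary of change from baseline, where a reader cannot tell a change in the patient from a change in how the rating was made. Descriptive tables are the only efficacy output this SAP plans, so their readability is what is at stake.

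**Working it through.** **Inputs.** Nine items, each scored 0 to 4 (Protocol section 9.2.17.3 and Appendix 3.2); MBA-9 at Visits 2, 7 and 9 (schedule of assessments); the LOCF rule (SAP section 6.1.7.1).

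**The plan's own figure.** Items by domain: 5 + 1 + 3 = 9. Maximum total: 9 × 4 = 36, as stated.

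**What each item needs.** The last column is my reading of the form.

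| Item | Content | How it can be rated |
|---|---|---|
| 1 | Motor skills (walking, hand use) | seen |
| 2 | Eye and social contact, as a share of time | seen |
| 3 | Sustained interest, as a share of time | seen |
| 4 | Reaching, as a share of time | seen |
| 5 | Chewing | history (labelled) |
| 6 | Speech | heard |
| 7 | Hand use | history (labelled) or assessment |
| 8 | Dystonia, by joints and limbs, up to fixed deformity | seen, perhaps felt |
| 9 | Hypertonia, with or without contractures | examined by hand |

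**Telephone.** Items 1, 2, 3, 4, 8 and 9 are affected: 6 × 4 = 24 of 36 points (67%). Items 5, 6 and 7 remain: 3 × 4 = 12 points. Check: 24 + 12 = 36.

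**Video.** Item 9 alone: 1 × 4 = 4 of 36 points (11%). With item 8: 2 × 4 = 8 of 36 points (22%).

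**Effect of LOCF.** Write x2, x7 and x9 for one item's score at Visits 2, 7 and 9.

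- Blank at Visit 7: x7 is set to x2, so the change is x2 − x2 = 0.
- Blank at Visit 9 but rated at Visit 7: x9 is set to x7, so the Visit 9 change repeats the Visit 7 change.
- Blank at both: x9 is set to x2, so the change is again 0.

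If all six items are blank at a telephone Visit 7, those 24 points contribute exactly zero change. Only the 12 points of items 5, 6 and 7 can move the total. The rule sets no minimum number of answered items for the MBA-9.

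**Size in the table.** If a share r of the ratings at a visit were remote, and each such total were shifted by b points on average, the visit mean would move by r × b. Neither r nor b is given in the documents, so I offer no figure.

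**The case against.** The permission is conditional. It applies only in special circumstances and where feasible; the investigator must discuss mitigation with the medical monitor and document the reason. Protocol section 9 requires assessments not done to be reported as such. Nothing obliges an investigator to score rigidity over the telephone. This stands, but an item properly left blank is then exposed to LOCF, so the safeguard on conduct leads into the problem in the analysis.

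The form is presented as an example, and no text forbids caregiver input on unlabelled items. This also stands: that six items need sight or examination is a reading of the form and not a rule in it.

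Affected patients can be traced. SAP section 9.4.6 lists them with a description of what was altered, SAP section 7.2 lists COVID-related deviations separately, and SAP section 6.1.10 puts all collected data in listings. None of these reaches the MBA-9 table, and a rating that section 9.3 permits need not appear as a deviation.

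Some stronger readings are tempting but not supported:

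- *All seven items without a history label (28 of 36 points) are lost by telephone.* Speech, item 6, can be heard.
- *Video is as bad as telephone.* By video only one or two items are in doubt.
- *The CGI-S and CGI-I tables have the same defect.* Protocol sections 9.1 and 9.2.17.2 base those ratings on the whole visit, but section 9.3 allows the visit itself to be virtual, and no part of either scale is shown to be unratable remotely.
- *The comparison with placebo is biased.* Allocation is randomised and double-blind, and nothing suggests that visit mode differs by arm.
- *The affected share must be large because the pandemic contributed to stopping the trial.* Stopping early could equally have left few late visits of any kind.

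**Conclusion.** The point holds for the MBA-9 and mainly for telephone visits: six of nine items, 24 of 36 points. For video it holds for item 9 and perhaps item 8, 4 to 8 points. SAP sections 8.3.3 and 6.1.7.1 together would present ratings from a different source, or carried-forward scores, as patient change.

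This rests on the item classification above and on Visit 2 having been rated in person. That the modes are pooled follows from the absence of any split; the SAP does not say so in terms.

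Severity is low. The MBA-9 is one of several other secondary endpoints, SAP section 8 excludes formal hypothesis testing, and no error rate or power is affected. How far any visit mean would move cannot be computed from the documents.

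**What to change.** 1. In SAP section 8.3.3, use the visit mode recorded in the eCRF to present MBA-9 change from baseline twice: for all visits, and without telephone-rated visits. Flag video visits.
2. In SAP section 6.1.7.1, state that LOCF does not apply to MBA-9 items that could not be rated because of visit mode. A total with such items is then missing; the items that were rated stay in the listings.

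The CGI tables need no change on this argument.

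The cost is SAP wording, one extra table and a filter on information already collected. The restricted table will have fewer values at Visits 7 and 9. Leaving out telephone visits could also select by site or by patient condition, which is why the all-visits table should stay beside it. If unblinded tables already exist, the added table should be labelled post hoc, as SAP section 1 requires of unplanned analyses.
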